After completing three baseline trials of the DRUID app participants will schedule their testing sessions. The PI or RA will assign their ID code (sequentially) and will provide the participant with contact information of a CBG producer who will ship color-coded vials of hemp derived CBG and placebo directly to them. Finally, participants will be instructed to abstain from using any cannabis products including CBG for a minimum of 24 hours prior to their testing session.

Testing Sessions: Approximately one-week after the pre-testing Zoom session, participants will meet with a RA (blinded to the color-codes used for the drug and placebo) on Zoom for their first testing session. First, the RA will confirm that participant has abstained from use of cannabis or CBG for a minimum of 24 hours prior to the testing session. As depicted in Figure 1, participants will then provide baseline (T0) ratings of their subjective state (anxiety, stress, mood). Specifically, participants will rate their subjective levels of anxiety and stress using 0 (not at all) to 10 (extremely) visual analogue scales, and they will rate their subjective mood using a 0 (extremely negative) to 10 (extremely positive) visual analogue scale. They will also complete the state form of the State-Trait Anxiety Inventory, which assesses symptoms of anxiety participants are experiencing in the moment [12].

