Next, participants will be instructed to ingest one of the color-coded vials. Half the participants (those assigned odd ID codes) will be assigned to ingest the blue vial containing 20mg CBG first and the other half (those assigned even ID codes) will be assigned to ingest the yellow vial containing 20mg placebo first. The CBG tincture is composed of 10 mg/ml CBG, 0.89 mg/ml CBGA, beta-caryophyllene 0.35 mg/ml (0.51 mg/ml total terpenoids). It is derived from a CBG-dominant hemp plant containing less than the 0.3% THC limit imposed in the U.S. Agricultural Improvement Act of 2018. Single 3ml amber vials will be prepared with this material containing 2ml each representing a dose of 20mg of CBG. Chartreuse liqueur (55% ethanol by volume) prepared by Les Peres Chartreux, France 1ml, diluted with 1ml filtered water will be employed as the placebo as it provided a reasonable match for the green color and herbal/ethanol taste of the CBG tincture. Opaque vials will be labeled with color coded tabs (Blue = CBG, Yellow = Placebo) in double-blind fashion and mailed directly to study participants. To dilute the taste, participants will be instructed to mix the contents of the vial in a small glass of water prior to ingestion.

After observing the participant orally ingest the product, the RA will instruct them to complete an online survey that contains measures of their demographic characteristics; anxiety, depression, and stress levels; as well as their cannabis and CBG use patterns. Specifically, participants will be asked to provide information pertaining to their gender, age, ethnicity, education, personal income, work status, and marital status. They will also complete the Daily Sessions, Frequency, Age of Onset, & Quantity of Cannabis Use Inventory (DFAQ-CU) which is a 41-item inventory, with 24 core items that assess frequency, age of onset, and quantity of cannabis flower, quantity of cannabis concentrates, and quantity of edibles typically used [13]. The remaining items measure other aspects of cannabis use not commonly measured by other cannabis use scales (e.g., forms of cannabis; methods of administration; use for medical, recreational, or combined purposes). The

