online survey will also contain the State-Trait Anxiety Inventory (STAI) which measures state and trait anxiety [12]. The inventory contains two parts, one containing 20 items designed to assess state anxiety and another part containing 20 items designed to assess trait anxiety. The state anxiety section assesses how individuals feel in the moment, while the trait anxiety section assesses how individuals generally feel. Finally, participants will complete the Depression Anxiety Stress Scales (DASS-21) which will be used to assess levels of depression, anxiety, and stress [14]. Each of the three subscales contains seven statements and participants indicate how much each statement has applied to them in the past week.

After completing the online questionnaire, participants will provide T1 ratings of their subjective state and subjective drug effects. Specifically, participants will rate their subjective levels of anxiety and stress using a 0 (not at all) to 10 (extremely) visual analogue scales, and they will rate their subjective mood using a 0 (extremely negative) to 10 (extremely positive) visual analogue scale. They will also complete the state form of the STAI. They will rate their levels of intoxication using a 0 (not at all intoxicated) to 10 (extremely intoxicated) visual analogue scale, the level of drug effects they were experiencing using 0 (none) to 10 (a lot) visual analogue scale, and their liking of the drug effects using 0 (dislike very much), 5 (neutral) to 10 (like very much) visual analogue scale. They will also rate their level of dry eyes, dry mouth, sleepiness, appetite, and racing heart/heart palpitations using 0 (none) to 10 (extremely) visual analogue scales. The approximate time between T0 and T1 ratings will be 20 mins.

[figure not shown]

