Participants will subsequently complete the online Trier Social Stress Test (TSST) [15]. For this task, participants will be instructed to mentally prepare a 5-min speech describing why they would be a good candidate for their ideal job. They will be informed that the speech will be recorded and reviewed by a panel of judges trained in public speaking (although no such recording will be made). They will be sent to a Zoom breakout room for 10-mins to prepare their speech. The RA will put on a white lab coat while they are in the breakout room. Participants will be brought back to the main Zoom room and asked to deliver their speech to the RA who will maintain a neutral expression. They will be instructed to speak for the entire 5-min period and will be prompted to continue if they stop for more than 20 secs. Immediately upon completing the speech, they will be told they will need to complete a 5-min math test. For this test, they will be instructed to sequentially subtract the number 13 from 1,022. Each time they make a mistake they will be informed they made a mistake and will be instructed to start over from 1,022. Following the stress manipulation, participants will provide T2 ratings of their subjective state and subjective drug effects as described above. The mean time between T0 and T2 ratings will be approximately 45 mins.

Participants will then complete the California Verbal Learning Test-II (CVLT-II) [16] which assesses verbal free recall. Participants will be asked to listen to and immediately recall a list of 16 words three times in a row (Trials 1–3). They will then be asked to listen to and immediately recall a list of 16 new words (List B). Immediately following recall of List B, participants will be required to recall the words from List A (Short Delay). Alternate forms of the lists will be used in the first and second testing sessions to reduce practice effects. Immediately after completing the CVLT-II participants will complete the DRUID app. Finally, participants will provide T3 ratings of their subjective state and subjective drug effects as described above. The mean time between T0 and T3 ratings will be approximately 60 mins.

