One-week after the first testing session, participants will complete the second testing session. This session will be identical to the first testing session except those participants who ingested the blue vial containing CBG in the first session, will ingest the yellow vial containing placebo in the second session. Those who ingested the yellow vial containing placebo in the first session, will ingest the

blue vial containing CBG in the second session. Neither the participant nor the RA will know which color code corresponds to CBG and placebo.

Figure 1. Overview of Procedure for Each Testing Session

Safety Considerations

Risks of physical harm, discomfort, and psychological distress will be minimized by only recruiting individuals who have experience using cannabis-based products (have used these products at least 10 times) and by informing participants that they can skip questions they are not comfortable answering and cease tests they are not comfortable continuing. Our prior survey study on CBG indicates that CBG does not cause serious adverse reactions with only a minority of participants indicating they experience minor side effects (dry eyes, dry mouth, increase appetite, increased heart rate etc.). Nevertheless, participants who experience psychological distress will be provided with information about crisis lines and counseling services. If participants report any serious side effects from the CBG we will submit an adverse event report to the IRB and will cease further testing until guidance is provided from the IRB.

Follow-up

There are no plans to follow-up on participants unless they experience an adverse event.

Data Management and Statistical Analyses

Data Management: Data will be stored in a locked private office and on password protected encrypted computers. Prescreening data and survey data will be stored on Qualtrics and then downloaded onto a password protected encrypted computer. The Master list (linking ID codes to individual participants) will be stored on the PI's password protected encrypted WSU owned computer. The RA will enter the data into Excel on a password protected computer and data entry will be checked by an independent RA and/or the PI.

Power: Results of an a priori power analysis using G-Power indicate that a sample size of 34 will be required to achieve power of .80 to detect medium-sized effects (i.e., $d = 0.50$), with alpha set at .05.

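### The only IRB-reporting and pausing rule depends on a serious effect coming from CBG, which those present cannot judge under the blind and which, read literally, omits some serious events

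*Combined protocol and SAP*

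**What the plan says.** Under Safety Considerations, the plan commits to an IRB report and a pause on one condition: "If participants report any serious side effects from the CBG we will submit an adverse event report to the IRB". The same sentence adds that the team "will cease further testing until guidance is provided from the IRB". It sets no time limit and does not say who decides on cause.

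On blinding, the Testing Sessions text describes the RA as "blinded to the color-codes used for the drug and placebo" and later states: "Neither the participant nor the RA will know which color code corresponds to CBG and placebo". It also gives the code itself: "Opaque vials will be labeled with color coded tabs (Blue = CBG, Yellow = Placebo) in double-blind fashion". Odd ID codes take the blue vial first and even ID codes the yellow. Data Management places the list linking ID codes to people with the principal investigator (PI): "The Master list (linking ID codes to individual participants) will be stored on" a computer belonging to the PI. The text does not say whether the PI is blinded.

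Both sessions include the Trier Social Stress Test (TSST), which comes after the vial and the T1 ratings. Participants also rate possible side effects after dosing: "They will also rate their level of dry eyes, dry mouth, sleepiness, appetite, and racing heart/heart palpitations". These ratings are repeated at T2 and T3.

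**The concern.** A rule for reporting and pausing should be usable by the people present when something happens. This one requires them to know that the cause was CBG, and the design withholds that knowledge. It also requires the participant to be the source of the report.

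Two things are at stake. First, followed to the letter, the same serious event would lead to a report and a pause if ascribed to CBG, and to neither if ascribed to the placebo vial or the stress test. Second, the IRB might not hear of a serious event caused by a study procedure rather than by the product, although the stressor is part of what participants are asked to undergo. The plan's background notes that no clinical trials of CBG in humans had been published, so there was little outside experience on which to base a causal judgement.

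**Working it through.** No arithmetic bears on this point. The check sets the safety provisions side by side, asks who can apply the trigger, and then tries different events against its wording.

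**1. Safety and IRB provisions in the supplied text**

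- Safety Considerations, reporting sentence. Trigger: a participant reports a serious effect due to CBG. Action: IRB report and pause.
- Safety Considerations, distress. Trigger: any psychological distress. Action: crisis-line and counselling details. No report or pause.
- Safety Considerations, right to skip questions or stop tests. Action: protects the individual. No report or pause.
- Follow-up. Trigger: any adverse event, with no limit on cause. Action: follow-up, not described further. No report or pause.
- Ethics. The IRB appears only for approval before data collection.
- Testing Sessions, ratings at T1, T2 and T3. These help detection, but the text does not link them to a report or pause.

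So the first item is the only rule for reporting and pausing.

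**2. Who can apply the trigger**

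- The participant and the RA do not know which colour is CBG, so they cannot know whether CBG was taken in that session.
- The means to look up assignment exist (the colour code, the odd/even rule and the master list), but no process or judge of cause is described.
- Knowing the vial would not settle cause. The vial is taken before T1 (about 20 minutes after T0). The TSST follows, with 10 minutes of preparation, a 5-minute speech and a 5-minute subtraction task, and T2 comes at about 45 minutes. The exclusion criteria give panic attacks as an example of a serious CBG reaction. A panic attack during or after the TSST could come from either source.

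**3. Events tried against the literal wording**

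- Serious, reported by the participant, ascribed to CBG: covered.
- Serious, after the placebo vial: not covered, because it is not due to CBG.
- Serious, ascribed to the TSST in either session: not covered, for the same reason.
- Serious, seen by the RA but not reported by the participant: not covered, because the trigger is a participant's report.

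**4. Timing**

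The current sentence has no end point, and a replacement must not add one. Even-ID participants take placebo first and so take CBG in their last session. T3 is only about 60 minutes after T0. With half of the planned sample on even codes (34 / 2 = 17), a rule that stopped at the last session would drop late effects of the only CBG dose for about 17 people.

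**The case against.** The strongest reply is that a blinded team would not read the sentence literally. Session staff cannot ascribe an event to placebo, and because a vial always precedes the TSST they cannot rule out CBG for an event during it. The workable reading is that any serious event possibly due to the study product is reported. That would cover placebo-session events and many of those around the stressor. It is quite likely what the team would do, but the sentence does not require it, and the amendment would simply write that practice down.

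Other replies also carry weight:

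- The RA-only case is narrow. The session is live on Zoom, ratings are taken three times after dosing, and participants can report later. It does not vanish, since someone in acute distress may neither complete a rating nor report.
- A serious event caused by the placebo itself is remote: 1 ml of liqueur at 55% ethanol holds 1 x 0.55 = 0.55 ml of ethanol.
- The consent form and the IRB's conditions are outside the supplied text and may impose wider duties.
- People with prior serious reactions to CBG are excluded. This helps less than it seems, because entry requires experience with cannabis products, not with CBG, so some participants may have no CBG history to screen.

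A reader might infer that the rule endangers the blind: someone would check assignment before halting, and the decision would reveal the single colour code. The documents describe no such check, so this is not part of the finding. A reader might also fault the lack of rating levels that trigger a report. The TSST is meant to raise stress, so such levels could be crossed by design, and their absence is not a defect here.

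**Conclusion.** The point holds as a minor defect of wording, worth correcting but not a flaw in the trial's conduct. The sole reporting and pausing rule rests on a causal judgement that those present cannot make, and read literally it omits three kinds of serious event.

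Its size cannot be estimated, because no serious-event rate is given. The number of events left out is probably very small given a single 20 mg dose in experienced cannabis users. A reader might take the number of placebo sessions, or of sessions with a stress test, as a measure of the gap. Those counts describe the design. They say nothing about how often a serious event would occur and go unreported. Nor does the text show that any event was withheld: a narrow trigger is not an instruction to stay silent.

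The conclusion assumes a literal reading and that no wider duty exists in the consent form or IRB conditions. Confidence is medium for that reason. The document already reports results, so the point applies to the plan's wording and to any repeat of the design.

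**What to change.** Replace the trigger in Safety Considerations with: *any serious adverse event reported by a participant or observed by study staff after either vial or during any study procedure, including after the last session, regardless of vial assignment.*

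Then separate the two actions. Report every such event to the IRB. Cease testing until the IRB gives guidance, unless the event is clearly unrelated to both the study product and the study procedures, with that judgement made without unblinding session staff. Keeping the exception avoids halting the study for, say, an unrelated hospital admission in the washout week.

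The cost is one or two sentences. The downside is possibly a few more reports, or a pause for an event that proves to have followed placebo or to be due to the stressor. No change to the analysis, sample size or visit schedule is needed.

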Research Protocol

General Information

Protocol Title: Acute Effects of Cannabigerol

Protocol Number: NCT05257044

Protocol Registration Location and Date: clinicaltrials.gov (25/02/2022)

Document Date: August 10, 2024

Project Summary

Cannabigerol (CBG) is a phytocannabinoid increasing in popularity, with preclinical research indicating it has anxiolytic and antidepressant effects. However, there are no published clinical trials to corroborate these findings in humans. Therefore, the primary objective of this study is to examine the acute effects of CBG on anxiety, stress, and mood. Secondary objectives are to examine whether CBG produces subjective drug effects or motor and cognitive impairments. We will assess these objectives using a double-blind, placebo-controlled cross-over field trial with 34 healthy adult participants with experience using cannabis. Participants will complete two sessions (with a one-week washout period) via Zoom. In each, they will provide ratings of anxiety, stress, mood, and subjective drug effects prior to double-blind administration of 20mg hemp derived CBG or placebo tincture (T0). These ratings will be collected again after participants orally ingest the product and complete an online survey (T1), again after they complete the Trier Social Stress Test (T2), and again after they complete a verbal memory test and the DRUID impairment app (T3). We hypothesize that CBG will decrease anxiety, decrease stress, and elevate mood. Further, we hypothesize that ratings of subjective drug effects will be low and that CBG will not produce motor or cognitive impairments.

Rationale and Background

The rapid proliferation of the new legal cannabis market has instigated producers to cultivate an array of novel products to satisfy consumers' growing interest. While products high in delta-9-tetrahydrocannabinol (THC) continue to saturate the market [1], a growing body of consumers are seeking alternative non-intoxicating products carrying the promise of easing what ails them. Producers are responding to this demand by isolating various minor phytocannabinoids and marketing them with bold, but largely unsubstantiated, claims of their therapeutic potential. While cannabidiol (CBD) continues to be the dominant non-intoxicating cannabinoid of interest to both consumers and researchers, cannabigerol (CBG) is rapidly increasing in popularity [2].

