Data Analysis Plan: Pairwise deletion will be used to handle the small amount of missing data anticipated. Alpha will be set to .05 and effect sizes of 0.01 will be interpreted as small, 0.06 will be considered medium, and 0.14 and above will be considered large. Data will be analyzed using IBM SPSS v.27.

Percentages, means, and standard deviations will be used to determine the demographic characteristics and cannabis use patterns of the sample. Mean DASS subscale scores, mean subjective state (mood, anxiety, stress) ratings, mean STAI state and trait anxiety scores, and mean

subjective drug effect ratings will be computed at baseline (T0) for each condition.

Change scores will be created by subtracting baseline (T0) scores from T1, T2, and T3 scores for the subjective state ratings (anxiety, stress, mood), STAI state anxiety scores, and subjective drug effect ratings (dry eyes, dry mouth, sleepiness, appetite, heart palpitations/racing heart).

Primary Outcomes: To assess the primary outcome (determine the effects of CBG vs. placebo on anxiety, stress, and mood) a series of 2 x 3 repeated-measures ANCOVAs will be conducted with condition (CBG, placebo), and time (T1, T2, T3) as within-subjects factors, order of drug administration as a covariate, and changes (difference from T0 to T1, T2, T3) in ratings of anxiety, stress, and mood as separate dependent variables.

Secondary Outcomes: To assess the effects of CBG on subjective drug effect ratings (dry eyes, dry mouth, sleepiness, appetite, heart palpitations/racing heart) a series of 2 x 3 repeated-measures ANCOVAs will be conducted with condition (CBG, placebo), and time (T1, T2, T3) as within-subjects factors, order of drug administration as a covariate, and changes (difference from T0 to T1, T2, T3) in these subjective drug effect ratings as the dependent variables.

To determine the effects of CBG vs. placebo on intoxication, drug effect, and drug liking ratings a series of 2 x 3 repeated-measures ANCOVAs will be conducted with condition (CBG, placebo), and time (T1, T2, T3) as within-subjects factors, order of drug administration as a covariate, and ratings of each indicator of drug effects as the dependent variables.

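### Minor, low-cost improvement for an open or reused protocol: add one open question on unwanted effects after T3 and one about a day later, because the plan otherwise relies on volunteered reports

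*Combined protocol and SAP*

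**What the plan says.** **After the session.** The Follow-up section reads "There are no plans to follow-up on participants unless they experience an adverse event". The action rule under Safety Considerations begins with the participant: "If participants report any serious side effects from the CBG we will submit an adverse event report to the IRB", after which testing stops until the IRB gives guidance.

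**During the session.** For the last assessment, Testing Sessions states "The mean time between T0 and T3 ratings will be approximately 60 mins". At T1, T2 and T3 participants rate five named side effects, and also intoxication, strength of drug effect and drug liking. Anxiety, stress, mood and STAI state anxiety are rated at the same points. Verbal memory and DRUID impairment are tested before T3. No open question about other unwanted effects is described.

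**One week later.** Apart from the vial, "This session will be identical to the first testing session". Session 2 therefore adds no question about the week in between. It does repeat the DASS-21, which covers depression, anxiety and stress over the past week. It apparently also repeats the five side-effect ratings before dosing: the Project Summary places drug-effect ratings at T0 and the Data Analysis Plan computes side-effect changes from T0, although Testing Sessions lists only subjective state and the STAI at that point.

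**After session 2.** No contact is scheduled.

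**Stated reasons for light follow-up.** The protocol cites low expected risk from a single dose, experienced cannabis users, exclusion of people with earlier serious reactions to CBG, and the team's own survey of CBG users.

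**The concern.** Follow-up is conditional on an adverse event, but no step is described that would find one after the first hour unless the participant makes contact. The session-2 visit helps only the CBG-first half, and only for named symptoms or low mood that persist; a resolved or unlisted effect would not appear. For the CBG-second half there is no later visit at all.

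This matters because Expected Outcomes presents the trial as the first objective look at both benefits and harms of CBG in people, and intends the results to inform users about risk. The low-risk rationale rests partly on the team's survey, whose findings the Rationale itself says need confirming in controlled trials. At stake is how far a lack of reported unlisted or later effects can be read as reassurance. The Data Analysis Plan describes no listing of such reports by condition.

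**Working it through.** **The plan's own figure.** The Power paragraph gives N = 34 for power .80, d = 0.50 and alpha .05. A paired t-test, taken as two-sided (the plan does not say), has power 0.808 at N = 34, and 34 is the smallest N that reaches .80. The figure reproduces and is not in dispute.

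**People without later contact.** Half the sample takes CBG second: 34/2 = 17 if all complete. The reported primary F(1, 32) with one covariate is consistent with 34 analysed (34 − 2 = 32).

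**Inputs assumed, because the documents do not give them.** Let p be the true rate after CBG of an unlisted or later effect, and q the fraction of affected people who would report it unprompted. When asked, everyone affected is taken to report it.

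**Chance of at least one report.**
- All n asked: 1 − (1 − p)^n
- Nobody asked: 1 − (1 − pq)^34
- Only the 17 CBG-second participants asked, the other 17 left to volunteer: 1 − (1 − p)^17 × (1 − pq)^17

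With p = 5%, asking all 34 gives 1 − 0.95^34 = 82.5%. Against that:

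| q | pq | Nobody asked | CBG-second half asked | All 34 asked |
|---|---|---|---|---|
| 25% | 0.0125 | 34.8% | 66.2% | 82.5% |
| 50% | 0.0250 | 57.7% | 72.8% | 82.5% |
| 75% | 0.0375 | 72.7% | 78.2% | 82.5% |
| 90% | 0.0450 | 79.1% | 80.9% | 82.5% |

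The gain from asking everyone runs from 82.5 − 34.8 = 47.7 points down to 82.5 − 79.1 = 3.4 points. It depends almost entirely on q.

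**Other rates, all 34 asked.** 28.9% at p = 1%, 49.7% at 2%, 97.2% at 10%. With an assumed 80% response (27 of 34), the 5% figure falls from 82.5% to 1 − 0.95^27 = 75.0%.

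**What no reports would mean.** With zero events among n people who were asked and answered, the one-sided 95% upper bound on the rate is 1 − 0.05^(1/n): 8.4% for n = 34, 10.5% for n = 27, 16.2% for n = 17. Without asking, the same silence bounds only the product pq, not p.

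**Could the listing by condition serve as a test?** Effectively not. An exact two-sided McNemar test needs at least six discordant pairs, all in one direction (five: 2 × 0.5^5 = .0625; six: 2 × 0.5^6 = .031). Even with no such reports on placebo, the chance of six or more among 34 is 0.6% at p = 5% and 11.9% at p = 10%.

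**The case against.** The strongest reply is that nothing in the plan is wrong. The trial is titled and framed around acute effects. The side-effect objective is a closed list of five items, each rated through T3 and compared with placebo, which is the kind of corroboration the Rationale asks for. The follow-up choice is disclosed and reasoned. All of that stands, and it is why this is an optional improvement and not a defect.

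Three stronger readings are tempting, and the documents do not support them.
- A reader might infer that every unlisted effect goes unrecorded unless volunteered. Up to T3 that is too strong. Strength of drug effect, intoxication and liking are actively rated; worsening anxiety, stress or mood would show; memory, balance and motor function are tested. These measures can register that something happened without saying what.
- A reader might infer that volunteered reports have no denominator. They have one: the participants dosed with CBG. The unknown is the reporting fraction q.
- A reader might take 82.5% as the benefit of asking. It is not. The benefit is the difference from what volunteering would have produced, and that may be small.

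It is also fair that the consent pages and Figure 1 are not in the text available. An end-of-session check could appear there, although a mere instruction to report problems would still produce volunteered reports. Finally, results are already reported in the document, so this trial's data collection cannot change.

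**Conclusion.** The point holds as a minor, inexpensive improvement to safety ascertainment, for a protocol that is still open or is reused. No open question on unwanted effects is described, ascertainment after T3 depends on volunteered reports, and 17 of 34 participants (if all complete) have no scheduled contact after their CBG session.

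For an assumed 5% effect with full reporting when asked, the gain in the chance of at least one report is about 48 points if a quarter of those affected would volunteer, and about 3 points if 90% would. The more dependable benefit is interpretive: silence from 34 people who were asked and answered bounds the rate at 8.4%, whereas silence from people who were not asked gives no bound without knowing q. Rare harms stay out of reach at this sample size either way.

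Nothing here shows that an effect was missed or that anyone was harmed. The primary analyses and the listed secondary objectives are unaffected.

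**What to change.** For an open or reused protocol:

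1. After the T3 ratings, ask one open question: whether the participant has noticed any unwanted effect since taking the vial.
2. About 24 hours later, send one automated Qualtrics link with the same question and one item on cannabis use since the session.
3. Do both at minimum after session 2, when all primary ratings are complete. Do them after both sessions, with identical wording and interval, if a small expectancy effect on session 2 is acceptable.
4. Do not put the question between T0 and dosing in session 2. The primary outcomes are "changes (difference from T0 to T1, T2, T3) in ratings of anxiety, stress, and mood as separate dependent variables", so any priming there would enter the change scores.
5. List the answers descriptively by condition, without a test. Let any positive answer trigger the existing follow-up and a serious one the existing IRB rule.

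**Cost.** A few lines of protocol text and one survey on a platform already in use; no extra staff or visits. The downsides are a small burden on participants, some non-response, and harder attribution if these regular cannabis users resume use after the session (the placebo session is the comparator, and the use item helps). Asking after both sessions carries the possible expectancy effect. Asking only after session 2 removes it but halves the CBG exposures queried from 34 to 17, with a zero-report bound of 16.2%, and makes the listing a comparison of 17 people on CBG with 17 others on placebo.
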